4.6 PHARMACOKINETIC AND PHARMACODYNAMIC ANALYSES

Several candidate PD biomarkers have been identified (e.g., FeNO, blood eosinophils, serum sST2, serum IL-5, plasma LIGHT, and serum amphiregulin) and will be measured to assess the effect of MSTT1041A on these biomarkers. Descriptive summaries of the

PD biomarker values at each visit, as well as changes from the randomization visit (absolute or percent change as appropriate), will be summarized by treatment arm.

The analyses of all PD endpoints will be based on the safety-evaluable population (see Section 4.1.2).

Serum MSTT1041A concentrations are measured at the following timepoints during the double-blind treatment period: Weeks 2, 6, 10, 14, 26, 38, 50, 54, and 70 (Predose, $C_{min,Wk4}$, $C_{min,Wk8}$, $C_{min,Wk12}$, $C_{min,Wk24}$, $C_{min,Wk36}$, $C_{min,Wk48}$, $C_{min,Wk52}$, follow-up concentration). The difference in the weeks for the concentration and the visit week is due to fact that study drug is given on Week 2 of the study, which is the start of the double-blind treatment period. In a subset of patients (approximately 20 per group), additional PK samples will be collected following first dose and at Week 26 for characterization of absorption and accumulation of MSTT1041A following SC administration. These concentrations will be tabulated and summarized using descriptive statistics (mean, standard deviation, coefficient of variation, median, minimum, and maximum) by treatment group and timepoint based on the safety-evaluable population (see Section 4.1.2). While treatment groups will be defined according to the actual treatment received, a review of dosing information including dosing errors, if any, and of the PK data for patients with unusual dosing patterns will be conducted to assess for any potential impact on the results.

Additional PK analyses of the double-blind treatment period data may be conducted as appropriate. Population PK modeling may be performed to characterize inter-individual variability, which may be reported separately from the clinical study report. Exploratory exposure-response analyses will be performed as appropriate, and may be reported separately from the clinical study report.

4.7 SAFETY ANALYSES

Safety will be assessed through the summary of adverse events, serious adverse events, adverse events of special interest, laboratory test results (hematology and serum chemistry, urinalysis), incidence of antibodies against MSTT1041A, ECG findings, and vital signs. Safety summaries for the 52-week double-blind treatment period will include outcomes as described in Section 2.1.4. This may include data collected at unscheduled visits, early termination visits, or safety follow-up visits.

Safety outcomes will be summarized based on the safety-evaluable population with patients grouped according to the actual treatment received (see Section 4.1.2). Safety summaries will be presented by treatment arm for all treated patients.

Safety assessments will also be conducted on the run-in safety-evaluable population, which consists of all patients who receive a placebo dose during the run-in period regardless of whether or not the patient is randomly allocated into the double-blind treatment period (see Section 4.1.3). These safety analyses will consider adverse

events that occur during the 2-week run-in period. Events that occur during this period will be followed until resolved.

4.7.1 Exposure to Study Medication

Exposure to study drug (number of study drug administrations and duration of treatment) will be summarized for the 52-week double-blind treatment period by treatment arm. Duration of treatment will be defined based on the difference (in days) between the dates of the first and last dose of study drug during the 52-week double-blind treatment period (Week 2 to Week 50 treatments) plus 29 days.

A listing of study drug administration with information on dosing errors during the placebo run-in and double-blind treatment periods will be provided.

4.7.2 Adverse Events

Verbatim descriptions of treatment-emergent adverse events will be coded using the latest version of MedDRA. A treatment-emergent adverse event is defined as any new adverse event or any worsening of an existing condition with an onset date on or after the first study drug administration date. Summaries of treatment-emergent events will be provided for each of the following categories:

- All adverse events
- All adverse events by most extreme severity
- Adverse events assessed as related to study treatment by the investigator
- All serious adverse events
- All suspected unexpected serious adverse events
- Adverse events that are a result of an error in study drug administration
- Adverse events leading to discontinuation of study treatment
- Adverse events leading to study discontinuation
- Adverse events of special interest

The adverse events of special interest will be identified as follows. Summaries will include tabulations by Medical Dictionary for Regulatory Activities (MedDRA) terms and listings, as appropriate.

- Cases of potential drug-induced liver injury that include an elevated alanine aminotransferase (ALT) or aspartate aminotransferase (AST) in combination with either an elevated bilirubin or clinical jaundice, as defined by Hy's law.
- Suspected transmission of an infectious agent by the study drug, as defined below
Any organism, virus, or infectious particle (e.g., prion protein transmitting transmissible spongiform encephalopathy), pathogenic or non-pathogenic, is considered an infectious agent. A transmission of an infectious agent may be suspected from clinical symptoms or laboratory findings that indicate an infection in

a patient exposed to a medicinal product. This term applies only when a contamination of the study drug is suspected.

- Potential major adverse cardiac events (MACE) will be identified as follows.

Death due to cardiovascular causes, non-fatal myocardial infarction, non-fatal stroke or transient ischemic attack (TIA), unstable angina or chest pain requiring hospitalization, coronary revascularization, and congestive heart failure (CHF) requiring hospitalization.

In addition, patient deaths and the primary cause of death will be listed, as well as any cases of pregnancy, anaphylaxis, anaphylactoid, and hypersensitivity.

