4.4 ASTHMA THERAPY AND CONCOMITANT THERAPY

Asthma medications used by the patient from 12 months prior to initiation of study drug (Week 0) through the end-of-study visit should be recorded on the appropriate eCRF. Other medications (e.g., prescription drugs, over-the-counter drugs, vaccines, herbal or homeopathic remedies, nutritional supplements) used by the patient within 3 months prior to screening through the end-of-study visit should be recorded on the Concomitant Medications eCRF.

Patients should not be asked to alter their standard therapy in any way until the informed consent process is complete.

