6.5 SAFETY ANALYSES

Safety analyses will be based on all patients who receive at least one dose of study drug during the 52-week double-blind treatment period with patients grouped according to the actual treatment received (MSTT1041A or placebo).

Safety will be assessed through summaries of adverse events, laboratory test results, ECGs, and vital signs. Verbatim descriptions of treatment-emergent adverse events will be coded, and their incidence will be summarized by treatment arm. A treatment-emergent adverse event is defined as any new adverse event reported or worsening of an existing condition on or after the first dose of study drug during the

MSTT1041A—Genentech, Inc.
88/Protocol GB39242, Version 4

52-week double-blind treatment period. In addition, separate summaries will be generated for serious adverse events, adverse events of special interest (AESI), deaths, pregnancies, malignancies, anaphylaxis events, major cardiac adverse events, adverse events leading to discontinuation from the study, and adverse events leading to discontinuation of study drug.

Safety assessments will also be conducted on all patients who receive a placebo dose during the run-in period, regardless of whether or not the patient is randomly allocated into the double-blind treatment period. These safety analyses will consider adverse events that occur during the 2-week run-in period and will be followed until the event is resolved.

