2.4 DATA INCLUDED IN WEEK 54 DATA CUT

The following data will be included in the Week 54 data cut:

- **For patients randomized to the 52-week double-blind treatment period:** All screening, run-in and post-baseline data with a clinical date (i.e., administration/assessment/onset/start date) on or before the date of randomization to Week 54 will be included.
- **For patients not randomized to the 52-week double-blind treatment period:** All screening and run-in data with a clinical date (i.e., administration/assessment/onset/start date).

The Week 54 data cut will include all data regardless of the type of study visit at which it was collected. This may include data collected at unscheduled visits, dosing termination visits, early termination visits, or safety follow-up visits, if the visit date was on or before the Week 54 data cutoff date.

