4.1.3 Run-In Safety-Evaluable Population

The run-in safety-evaluable population will include all patients who received the single-blind placebo dose during the run-in period (Week 0 treatment), regardless of whether or not the patient is randomly allocated into the double-blind treatment period. For safety analyses based on this population, only events that occur during the 2-week run-in period will be included. As placebo should be the only study drug administered during the run-in period, all patients will be grouped together for analyses based on this population.

In the rare event that a patient mistakenly receives MSTT1041A rather than placebo during the run-in visit, each dosing error will be reported as a major protocol deviation and reviewed in conjunction with the corresponding patient's safety data to assess for any impact on the overall safety conclusions.

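### SAP 4.7.2 omits the protocol's double-blind qualifier from the treatment-emergent rule, so read literally it admits about two weeks of pre-randomisation events into all four arms

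*SAP*

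**What the plan says.** SAP 4.7.2 defines a treatment-emergent event as a new event, or a worsening of an existing condition, "with an onset date on or after the first study drug administration date". It names no study period and no end date. The rule in Protocol 6.5 reads "worsening of an existing condition on or after the first dose of study drug during the" and then names the 52-week double-blind treatment period. SAP 1 says that the SAP's analyses supersede the protocol's analysis plan.

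The documents do not use the term study drug in one sense only:

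- **Including the Week 0 placebo.** SAP 4.1.3: "As placebo should be the only study drug administered during the run-in period". SAP 4.7.1: "A listing of study drug administration with information on dosing errors during the placebo run-in and double-blind treatment periods will be provided". Protocol 4.4 collects asthma medications "from 12 months prior to initiation of study drug (Week 0"). The schedule in Protocol Appendix 1 also labels the Week 0 injection as single-blind study drug.
- **From Week 2 only.** SAP 2 lists study drug dosing as starting at the randomisation visit. SAP 4.6 explains its PK week numbering by saying that study drug is given at Week 2.

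The safety tables group patients by the treatment actually received in the double-blind period (SAP 4.1.2 and 4.7). Run-in events also have their own population and summary (SAP 4.1.3).

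**The concern.** The treatment-emergent flag decides which events appear in every main adverse event table. If its clock starts at Week 0, an event after the single-blind placebo injection, such as an injection-site reaction, is tabulated under the arm to which the patient is later randomised. For about three patients in four that is an active dose they had not yet received.

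Four things would follow:

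- Every arm gains events that treatment cannot have caused, which pulls a ratio between arms towards 1. For a safety comparison that is the unwelcome direction.
- Placebo-only events are shown under 70, 210 or 490 mg.
- Run-in events in randomised patients are reported twice, in the run-in summary and in the treatment-emergent tables.
- The event window starts two weeks before the exposure window, because SAP 4.7.1 measures treatment duration from the Week 2 dose.

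**Working it through.** The documents give no figure to reproduce here. The check is a comparison of definitions, followed by a calculation of scale.

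**1. Does the SAP state the qualifier when it means double-blind dosing?** Yes. The mITT population (4.1.1), the safety-evaluable population (4.1.2) and treatment duration (4.7.1) all limit dosing to the double-blind period. Section 4.7.2, directly after 4.7.1, does not.

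**2. Would run-in events be available to flag?** Yes. Protocol 5.3.1 has all adverse events reported once study drug is initiated, and sets a reporting period for patients who receive only the run-in placebo.

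**3. Does any other rule remove them?** None found. SAP 4.1.3 limits the run-in population's analyses to run-in events. It does not bar those events from the safety-evaluable tables. SAP 4.7 labels its summaries as double-blind but sets no onset-date rule.

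**4. Share of the window.** Inputs: a 2-week run-in with a ±5-day window, so 9 to 19 days (Protocol Appendix 1, footnote b); 52 weeks = 364 days of treatment; 13 double-blind doses (SAP 4.1.2); 502 randomised (SAP 2.2).

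- To Week 54: 2/54 = 3.7%. Range: 9/(9 + 364) = 2.4% to 19/(19 + 364) = 5.0%.
- To Week 70, since 4.7.2 has no end date: 2/70 = 2.9%.
- Dosing occasions: 1/(13 + 1) = 7.1%.
- Observation added: 502 × 2/52 = 19.3 patient-years, of which 3/4 × 19.3 = 14.5 are in the active arms and 4.8 in placebo.

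**5. Effect on a risk ratio (illustration).** The documents give no adverse event rates, so these are assumptions: a constant hazard; 52-week placebo incidence p0 of 5%, 20% or 70%; a true hazard ratio HR of 2.0; and a run-in hazard m times the placebo hazard in every arm, with m = 1 or 3.

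- Weekly placebo hazard: h = −ln(1 − p0)/52.
- Placebo incidence with run-in: 1 − exp(−h(52 + 2m)).
- Active incidence with run-in: 1 − exp(−h(52·HR + 2m)).

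For p0 = 20%, the double-blind window gives 36.0%/20.0% = 1.80. With run-in at m = 1 it is 36.55%/20.68% = 1.77. At m = 3 it is 37.63%/22.03% = 1.71.

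| p0 | Risk ratio from Week 2 | From Week 0, m = 1 | From Week 0, m = 3 |
|---|---|---|---|
| 5% | 1.95 | 1.91 | 1.85 |
| 20% | 1.80 | 1.77 | 1.71 |
| 70% | 1.30 | 1.28 | 1.25 |

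With HR = 1.5 and p0 = 20%, the ratio goes from 1.42 to 1.41 (m = 1) or 1.37 (m = 3). Every case moves towards 1, and the movement is small.

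**The case against.** The strongest reply is that the intended rule can be read from the rest of the SAP. Sections 2 and 4.6 place study drug at Week 2. Section 4.7 frames its output as double-blind summaries. The safety-evaluable population requires a double-blind dose. Run-in events have a population of their own, which makes little sense if they are also meant to sit in the main tables. The protocol states the limit outright. On this view the SAP has lost a phrase, not changed a rule.

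Much of this stands. The Week 0 reading is one of two, and the documents do not show that the tables will include run-in events. What remains is that 4.7.2 is the operative definition, that it takes precedence over the protocol, and that the SAP's own safety sections apply the term study drug to the run-in dose.

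Three stronger readings are tempting, and the documents do not support them:

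- **That the events fall only on the active arms.** They would enter placebo too, balanced in expectation by randomisation. This is dilution, not bias against active drug.
- **That the Week 54 data cut sets the flag.** SAP 2.4 does include "All screening, run-in and post-baseline data with a clinical date", but that governs extraction. Run-in data are needed there for the run-in summary, and screening data are in the cut as well.
- **That a condition starting in run-in loses its pre-existing status.** Protocol 5.3.5.9 defines pre-existing by presence at the screening visit. Such a condition is not pre-existing under either reading of 4.7.2.

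**Conclusion.** The point holds as a defect in the wording of an operative rule. Applied literally, SAP 4.7.2 starts the treatment-emergent window about two weeks before randomisation in all four arms, contrary to Protocol 6.5. This rests on reading the first study drug date as Week 0, which the text allows but does not compel.

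If that reading were used, the effect would be small: 3.7% of the window to Week 54 (2.4% to 5.0% over the permitted run-in lengths), and a fall in the risk ratio of about 0.01 to 0.10 across the cases shown. Those ratios depend on the assumed incidences, hazard ratios and run-in hazards. The patient-years describe the observation added and are not an effect on the comparison. The misattributed rows, the double reporting and the mismatch with exposure would arise whatever the rates, provided some run-in events occur in randomised patients. A correction is warranted because the rule governs the main safety tables and costs almost nothing to repair.

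**What to change.** In SAP 4.7.2, restore the protocol's limit: an event is treatment-emergent if its onset or worsening falls on or after the date of the first dose in the 52-week double-blind period (Week 2). Add that run-in onsets in randomised patients are reported only in the run-in safety-evaluable summary, unless they worsen after that first double-blind dose. Check that the programming specification takes its reference date from the Week 2 dose.

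The cost is one or two sentences, with no new data and no loss of information, since run-in events keep their own summary. SAP 1 allows no changes at or after the 54-week analysis, so the edit has to precede it. If that analysis has already been run, the report should state which date was used.

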4.5.11 Asthma Exacerbations

At each study visit, the investigator will ask directed questions to assess whether the patient experienced any asthma exacerbations as defined in Appendix 12 since the last study visit.

Given that asthma exacerbations are the primary endpoint in this study, a dedicated eCRF will be used to record information regarding asthma exacerbation events. An asthma exacerbation must also be reported as an adverse event (or serious adverse event as applicable) (refer to Section 5 for more details). Sites should record all medications used for treatment of the asthma exacerbation in the appropriate eCRF.

Patients who experience symptoms consistent with an asthma exacerbation should be asked to come to the clinic for an unscheduled visit if possible. Patients will be asked to bring from home a urine sample collected at symptom onset. Additional evaluations will be performed as outlined in the schedule of activities (Appendix 1).

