5.2.2 Serious Adverse Events (Immediately Reportable to the Sponsor)

A serious adverse event is any adverse event that meets any of the following criteria:

- Is fatal (i.e., the adverse event actually causes or leads to death)
- Is life threatening (i.e., the adverse event, in the view of the investigator, places the patient at immediate risk of death)

This does not include any adverse event that had it occurred in a more severe form or was allowed to continue might have caused death.

- Requires or prolongs inpatient hospitalization (see Section 5.3.5.11)
- Results in persistent or significant disability/incapacity (i.e., the adverse event results in substantial disruption of the patient's ability to conduct normal life functions)
- Is a congenital anomaly/birth defect in a neonate/infant born to a mother exposed to study drug
- Is a significant medical event in the investigator's judgment (e.g., may jeopardize the patient or may require medical/surgical intervention to prevent one of the outcomes listed above)

The terms "severe" and "serious" are not synonymous. Severity refers to the intensity of an adverse event (e.g., rated as mild, moderate, or severe, or according to World Health Organization Adverse Drug Reaction Terminology (WHO-ART); see Section 5.3.3); the event itself may be of relatively minor medical significance (such as severe headache without any further findings).

Severity and seriousness need to be independently assessed for each adverse event recorded on the eCRF.

Serious adverse events are required to be reported by the investigator to the Sponsor immediately (i.e., no more than 24 hours after learning of the event; see Section 5.4.2 for reporting instructions).

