5.3.5.10 Lack of Efficacy or Worsening of Asthma

Medical occurrences or symptoms of deterioration that are anticipated as part of asthma should be recorded as an adverse event if judged by the investigator to have unexpectedly worsened in severity or frequency or changed in nature at any time during the study (e.g., an asthma exacerbation). When recording an unanticipated worsening of asthma on the Adverse Event eCRF, it is important to convey the concept that the condition has changed by including applicable descriptors (e.g., "accelerated worsening of asthma").

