5.6 ADVERSE EVENTS THAT OCCUR AFTER THE ADVERSE EVENT REPORTING PERIOD

The Sponsor should be notified if the investigator becomes aware of any serious adverse event that occurs after the end of the adverse event reporting period (*see Section 5.3.1*), if the event is believed to be related to prior study drug treatment. These events should be reported through use of the Adverse Event eCRF. However, if the EDC system is not available, the investigator should report these events directly to the Sponsor or its designee, either by faxing or by scanning and emailing the paper Clinical Trial Serious Adverse Event/Adverse Event of Special Interest Reporting Form using the fax number or email address provided to investigators.

5.7 EXPEDITED REPORTING TO HEALTH AUTHORITIES, INVESTIGATORS, INSTITUTIONAL REVIEW BOARDS, AND ETHICS COMMITTEES

The Sponsor will promptly evaluate all serious adverse events and adverse events of special interest against cumulative product experience to identify and expeditiously communicate possible new safety findings to investigators, IRBs, ECs, and applicable health authorities based on applicable legislation.

To determine reporting requirements for single adverse event cases, the Sponsor will assess the expectedness of these events using the following reference documents:

- MSTT1041A Investigator's Brochure

The Sponsor will compare the severity of each event and the cumulative event frequency reported for the study with the severity and frequency reported in the applicable reference document.

Reporting requirements will also be based on the investigator's assessment of causality and seriousness, with allowance for upgrading by the Sponsor as needed.

Certain adverse events are anticipated to occur in the study population at some frequency independent of study drug exposure and will be excluded from expedited reporting. These anticipated events include, but are not limited to, the following:

- Asthma exacerbations
- Symptoms assessed as relate to asthma (e.g., cough, wheezing, dyspnea, bronchospasm)

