Appendix 11 Compliance With Asthma Controller Medication

[Included in evening daily from screening through Week 54]

Did you take your preventive inhaler (medications) today?

Yes

No

Appendix 12

Definition of Asthma Exacerbation for Inclusion Criteria and Reporting of Adverse Events

Asthma exacerbation is defined as new or increased asthma symptoms (wheezing, coughing, dyspnea, chest tightness, and/or nighttime awakenings due to these symptoms) that result in one or both of the following:

- Hospitalization or emergency department, urgent care visit or urgent unscheduled office visit requiring administration of asthma treatment, such as bronchodilators and/or systemic corticosteroids, in addition to baseline controller medications
- Treatment with systemic corticosteroids for ≥ 3 days or a long-acting depot corticosteroid preparation with a therapeutic effectiveness of ≥ 3 days

Severe asthma exacerbation is defined as asthma symptoms requiring hospitalization or resulting in death attributed to asthma.

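### The pooled AE, severity and SAE summaries all include asthma exacerbations and none is planned without them, so a drug that works can offset a moderate excess of other events in those totals

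*SAP*

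**What the plan says.** - **Exacerbations are AEs.** Protocol 4.5.11 gives exacerbations a dedicated eCRF and adds: "An asthma exacerbation must also be reported as an adverse event (or serious adverse event as applicable". Protocol 5.3.5.10 is looser: worsening asthma "should be recorded as an adverse event if judged by the investigator to have unexpectedly worsened in severity or frequency", but an exacerbation is its own example.
- **The AE definition is the broad one.** Protocol Appendix 12 is titled "Definition of Asthma Exacerbation for Inclusion Criteria and Reporting of Adverse Events". Beyond the primary endpoint it counts urgent care and urgent unscheduled office visits, and bronchodilator treatment can suffice without systemic corticosteroids.
- **When they are serious.** Among the seriousness criteria in protocol 5.2.2 is an event that "Requires or prolongs inpatient hospitalization".
- **What is tabulated.** SAP 4.7.2 introduces nine categories with "Summaries of treatment-emergent events will be provided for each of the following categories". They include all AEs, AEs by worst severity and all SAEs. Protocol 6.5 says "separate summaries will be generated for serious adverse events, adverse events of special interest (AESI), deaths, pregnancies, malignancies, anaphylaxis events", and continues with major cardiac events and discontinuations. Neither list has a version without exacerbations.
- **The one exclusion.** Protocol 5.7 treats exacerbations as anticipated events that occur "independent of study drug exposure and will be excluded from expedited reporting". That governs reporting to authorities, not tabulation.
- **Coding.** "Verbatim descriptions of treatment-emergent adverse events will be coded using the latest version of MedDRA" (SAP 4.7.2). Tabulation by MedDRA term is mentioned there only in the paragraph on events of special interest.

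**The concern.** The safety objective compares drug with placebo, and the pooled AE and SAE lines are usually the first things read. Here those lines contain the event the drug is meant to prevent. A fall in exacerbations therefore lowers the active arm's totals, and an increase in other events can be cancelled by it.

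This matters most for harm spread thinly over many terms. Protocol 5.1.1.4 names weaker protection against infection, and unanticipated immune-mediated effects, as potential risks. Infection in general is not an event of special interest; only suspected transmission of an agent by the study drug is. With about 125 patients per arm, diffuse harm of this kind may not stand out in any single term. Severity is exposed too: where Table 5 of protocol 5.3.3 applies, a need for medical intervention or therapy is part of grade 3, which fits many qualifying exacerbations.

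**Working it through.** **Inputs.** From protocol 6.1 and SAP 2.2: placebo rate 0.63 per patient-year, 40% reduction (active rate 0.63 × 0.60 = 0.378), no over-dispersion (SAP), 15% dropout, two-sided 0.05. From protocol 4.1: 125 patients per arm. Assumed, because the documents do not give them: the incidence of other AEs and SAEs, the hospitalised share of exacerbations, and independence between exacerbations and other events.

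**1. The plan's own figure.** With t = 125 × 0.85 = 106.25 patient-years per arm and the null variance taken at the placebo rate,

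power = Φ[(|ln 0.6| − 1.96 √(2/(0.63t))) / √(1/(0.63t) + 1/(0.378t))] = Φ[(0.511 − 0.339)/0.200] = 80.6%.

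This agrees with the stated 80%. A Wald test with the same loss gives 72.6%. The power is not in dispute here; the rates are what is carried forward.

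**2. Exacerbations entering the AE tables.** Events over 106.25 patient-years: 66.9 placebo and 40.2 active, about 27 fewer. Patients with at least one in a full year:

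- placebo: 1 − exp(−0.63) = 46.7%
- active: 1 − exp(−0.378) = 31.5%
- gap: 15.3 points

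**3. Excess of other AEs that leaves any-AE equal.** Let p₀ and p₁ be the placebo and active proportions with another AE. Setting (1 − p₀)exp(−0.63) = (1 − p₁)exp(−0.378) gives

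p₁ − p₀ = (1 − p₀)(1 − exp(−0.252)) = 0.223 (1 − p₀).

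| Other AEs, placebo (assumed) | Any AE, both arms | Other AEs, active | Offset excess | Patients of 125 |
|---|---|---|---|---|
| 40% | 68.0% | 53.4% | +13.4 points | 16.7 |
| 50% | 73.4% | 61.1% | +11.1 | 13.9 |
| 60% | 78.7% | 68.9% | +8.9 | 11.1 |
| 70% | 84.0% | 76.7% | +6.7 | 8.4 |
| 80% | 89.4% | 84.5% | +4.5 | 5.6 |

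**4. Over-dispersion and dropout, at 60%.** With a negative binomial, P(no exacerbation) = (1 + kμ)^(−1/k).

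- k = 1: 38.7% v 27.4% have an exacerbation; offset excess +6.2 points.
- k = 2: 33.5% v 24.5%; offset excess +4.7 points.
- Mean time at risk cut to 0.85 year, no over-dispersion: 0.40 × (1 − exp(−0.252 × 0.85)) = +7.7 points.

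**5. SAEs.** If a share h of exacerbations is hospitalised and 5% of placebo patients have another SAE, the offset excess is 0.95 × (1 − exp(−0.252h)).

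- h = 5%: +1.2 points (1.5 patients of 125)
- h = 10%: +2.4 points (3.0 patients)
- h = 20%: +4.7 points (5.8 patients)

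**6. With the exclusion.** In the 60% row, the all-inclusive line reads 78.7% v 78.7% and the line without exacerbations reads 60.0% v 68.9%. A two-sided 5% comparison of the latter would have only about 31% power, so the gain is that the difference can be seen, not that it is established.

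No figure is offered for the severity table, because the documents give no grade distribution.

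**The case against.** **The totals are not wrong.** A reader might infer that the pooled comparisons are biased. The documents do not support that. The endpoint is the incidence and severity of AEs, an exacerbation is an AE by protocol rule, and the totals estimate that endpoint correctly. No test is planned on them. The issue is how they are read.

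**Not every safety output is affected.** A reader might infer that no safety table leaves exacerbations out. The special-interest list in SAP 4.7.2 (potential Hy's law cases, suspected transmission of an infectious agent, potential major cardiac events) does not contain them. The table of suspected unexpected serious events probably does not, since protocol 5.7 calls them anticipated. Laboratory, ECG and vital-sign summaries stand apart. The discontinuation tables are a weak case: protocol 4.6.1 restricts reasons for leaving the study to withdrawn consent and loss to follow-up.

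**The pieces are visible elsewhere.** SAP 4.5.3 analyses exacerbations by arm under the AE-reporting definition, and severe ones separately. AEs are MedDRA-coded, so a large excess in one term could still be seen. The iDMC reviews all unblinded AEs. This stands in part. However, separate rates do not show how many patients had an AE other than an exacerbation, because that needs patient-level exclusion.

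**Exclusion can hide harm too.** Protocol 5.1.1.2 lists dyspnea, wheezing and bronchospasm among possible systemic reactions. If the drug worsened asthma, tables without exacerbations would lose that signal. This stands, and it rules out basing the main safety statement on the exclusion tables alone.

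**The size is contingent.** With no effect on exacerbations the offset is zero, and other-event incidence is assumed. Both are true, which is why a range is given.

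**Conclusion.** The concern holds for three outputs: all AEs, AEs by worst severity, and SAEs. Each includes exacerbations and none is planned without them, so a working drug lowers its own pooled totals and can offset a moderate excess of other events there.

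At the planning rates the offset is about 13 to 4.5 points in any-AE as the assumed placebo incidence of other AEs goes from 40% to 80%. At 60% with assumed over-dispersion it is about 5 to 6 points. For SAEs it is about 1 to 5 points under the stated assumptions. These figures rest on independence, a full year at risk (except in the dropout check) and the planned 40% reduction. Dropout, over-dispersion, or exacerbations clustering in patients who already have another AE would shrink them. The broader Appendix 12 definition would enlarge them if the drug also prevents those additional events.

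No planned inference is invalid. What is missing is an inexpensive supplementary view that makes the drug-versus-placebo safety comparison easier to interpret.

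**What to change.** In SAP 4.7.2, pre-specify supplementary summaries by arm that exclude asthma exacerbations, for:

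- all AEs
- AEs by most extreme severity
- SAEs

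Show them alongside the all-inclusive tables and state that the two are read together, neither replacing the other. Fix in advance how the excluded events are identified: either events on the exacerbation eCRF matched to their AE records, or a pre-specified list of asthma preferred terms. Protocol 4.5.11 describes two records and states no linking field, so the matching rule must be written down.

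SAP section 1 bars changes at or after the 54-week analysis, so this has to be added beforehand. An exclusion chosen after unblinding would also look selective. The cost is a few extra tables and the matching rule. The data are already collected, and no change to the protocol is needed.
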